12.2 Treatment Exposure

[REDACTED]

[REDACTED]

[REDACTED]

Although not captured directly on the CRF, additional variables related to study drug administration will also be derived for summarization:

- Study drug interruption (yes/no), where interruptions will be identified via presence of a TEAE where action taken with study drug was marked as 'drug interrupted' or a protocol deviation indicating study drug was interrupted
- Premature discontinuation of study drug (yes/no), where discontinuations will be identified via presence of a TEAE where action taken with study drug was marked as 'drug withdrawn' or a protocol deviation indicating study drug was prematurely discontinued. Subjects who discontinue the study prior to Visit 6 (Day 15) will also be reviewed to verify if study drug was prematurely discontinued or not.
- Study drug completion, defined as those subjects where premature discontinuation of study drug is not equal to 'yes'

A blinded data review will be conducted prior to database lock and unblinding to identify any other cases of study drug interruption or premature discontinuation of study drug which are known to have occurred, but are not identified through the criteria above. The classifications from this final review will be used for analysis.

Subject data listings will be generated to present details of study drug assignment, study drug replacement, as well as first instillation of study medication performed in-clinic on Day 1. Details from the study drug accountability assessment will also be listed.

13. Efficacy Analyses

13.1 Primary Analysis

The hierarchical primary efficacy measures are the absence of anterior chamber cells [REDACTED]

[REDACTED] and the absence of pain [REDACTED]

The anterior chamber cell count will be recorded as [REDACTED]

[REDACTED] Anterior chamber cell count is assessed for study eye only. Refer to

Table 2 for details.

Table 2. Anterior Chamber Cell Counts and Grade

Ocular pain will be assessed by the patient [REDACTED]

The observed anterior chamber cell count at Visit 6 will be used and categorized for analysis as follows:

- Absence of anterior chamber cells: [REDACTED]
- Presence of anterior chamber cells: [REDACTED]

Within this analysis, missing values for visits after a subject is discontinued for lack of efficacy or values obtained after subject has received rescue medication will be imputed as failures [REDACTED]

[REDACTED] for analysis. For all other missing data, LOCF will be used to impute the missing anterior chamber cell count grade, and the LOCF value will then be categorized for analysis as “cells present” or “cells absent”.

Derivation of the pain score and absence of pain [REDACTED] will follow the same approach for handling of missing data and handling of pain scores obtained following use of rescue medication.

The primary efficacy variables, the absence of anterior chamber cells at [REDACTED] and the absence of pain [REDACTED] will be summarized by [REDACTED]

For each OCS-01 dose (QD and BID) separately, the primary efficacy analyses will [REDACTED]

SAS® code used to generate the [REDACTED]

[REDACTED]

Comparison of OCS-01 QD versus placebo (vehicle) will be conducted in a similar manner, differing only by the treatment arms which are included within the comparison. Testing for each OCS-01 treatment group versus placebo (vehicle) for the absence of pain variable will use similar code.

[REDACTED]
[REDACTED]
[REDACTED]
[REDACTED]
[REDACTED]
[REDACTED]
[REDACTED]

Anterior chamber cell grade in the study eye at Visit 6 (Day 15) will be summarized by [REDACTED]

[figure not shown]
[figure not shown]
[REDACTED]
[REDACTED]

[figure not shown]
[figure not shown]
Ocular pain score at Visit 4 (Day 4) will be summarized by [REDACTED]

The primary efficacy analysis will be conducted using the FAS.

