concentration of dexamethasone from DexNP treatment was still 10-times higher than what was observed with Maxidex® treatment. These results demonstrate that dexamethasone, complexed with CD nanoparticles, elicits a higher concentration and longer duration of action in the tear fluid than the currently available product, Maxidex®. Importantly, DexNP was well tolerated by the subjects and no serious adverse events (SAEs) were observed.

A study conducted by Saari et al. ([Saari, Nelimarkka et al. 2006](#)) evaluated the efficacy of an eye drop containing 0.7% dexamethasone-CD suspension, applied once daily, compared to a 0.1% dexamethasone sodium phosphate eye drops, applied three times daily for the treatment of post-operative inflammation after cataract surgery. The dexamethasone-CD suspension was shown to be safe and more effective in treating post-operative inflammation, after once daily dosing, than 0.1% dexamethasone sodium phosphate eye drops applied three times daily.

In the human studies with DexNP to date, DexNP was well tolerated and the only AE reported has been a modest rise in intraocular pressure (IOP), a known side effect of dexamethasone use, which subsided following discontinuation of DexNP in all cases ([Kristinsson, Fridriksdottir et al. 1996](#)) ([Johannesson, Moya-Ortega et al. 2014](#)) ([Saari, Nelimarkka et al. 2006](#)) ([Tanito, Hara et al. 2011](#)) ([Ohira, Hara et al. 2015](#)) ([Krag and Hessellund 2014](#)) ([Shulman, Johannesson et al. 2015](#)).

Building on the enhanced ocular penetration of DexNP, as well as its favorable efficacy results and safety profile, Oculis has developed an updated formulation, OCS-01, consisting of water soluble 1.5% Dexamethasone- γ CD complexes to treat post-surgical inflammation.

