9.6.2 Discontinued subjects

Subjects may be discontinued prior to their completion of the study due to the following:

- AEs
- Protocol violations
- Subject's decision (e.g. withdrawal of consent)
- Administrative reasons (e.g. inability to continue, lost to follow up)
- Sponsor termination of study
- Principal Investigator's (PI) decision
- other

Note: In addition, any subject may be discontinued for any sound medical reason.

If at any time during the study the Investigator deems that the subject's safety has been compromised or the subject has been non-compliant, the subject may be withdrawn from the study.

Any subject who wishes to withdraw from the study for any reason is entitled to do so at any time without obligation.

Notification of a subject's discontinuation and the reason for discontinuation will be made to Ora and/or the Sponsor and will be clearly documented on the eCRF.

Any subject who discontinues study drug or who is administered rescue therapy will remain enrolled in the study and continue to participate in all subsequent visits for safety and efficacy assessments. If a subject discontinues participation in the study early, every attempt will be made to complete the exit procedures required at the final study visit (Visit 7).

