11.7 Handling of Missing Data

The primary analyses of all efficacy data will use last observation carried forward (LOCF) to impute missing data; data for visits after a subject is discontinued for lack of efficacy or receives

rescue medication will be imputed as failures for success/failure endpoints and will be imputed using LOCF for other endpoints. To check robustness of results, sensitivity analyses of the primary efficacy endpoints will include analyses of observed data only, imputing data from subject visits after discontinuation for lack of efficacy or receipt of rescue medication as failures. Tipping point analysis and multiple imputation methods using monotone methodology will also be used to impute missing data as additional sensitivity analyses. PP analyses will use observed data only, with the exception of subjects who have missing data due to discontinuation for lack of efficacy or for subjects who receive rescue medication; for these subjects, missing data after discontinuation or data after receiving rescue medication will be imputed as failures for success/failure endpoints and will be imputed using LOCF for other endpoints.

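### A subject who leaves the study for an adverse event before the endpoint visit, unrescued and with a clear last grade, is carried forward as a primary-endpoint success

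*SAP*

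**What the plan says.** The primary endpoints are absence of anterior chamber cells at Visit 6 (Day 15) and absence of pain at Visit 4 (Day 4) (Protocol 11.5.2). For cells, SAP 13.1 starts from observed data: "The observed anterior chamber cell count at Visit 6 will be used and categorized for analysis as follows". It then sets two exceptions that count as failures: "Within this analysis, missing values for visits after a subject is discontinued for lack of efficacy or values obtained after subject has received rescue medication". Everything else is carried forward: "For all other missing data, LOCF will be used to impute the missing anterior chamber cell count grade". The grade so obtained is classed as showing cells or showing none, in the same way as an observed one. Pain "will follow the same approach for handling of missing data and handling of pain scores obtained following use of rescue medication". The analysis set is the FAS.

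Protocol 11.7 has the same two failure cases, exit for lack of efficacy and rescue, and so does SAP 8.2.2. SAP section 16 declares no changes from the protocol-stated analyses.

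Protocol 9.6.2 opens its list of reasons for leaving with "Subjects may be discontinued prior to their completion of the study due to the following", and adverse events come first. Sections 6.6 and 9.6.2 of the protocol keep subjects who stop study drug or receive rescue in follow-up. For those who leave the study early, they ask sites to attempt the Visit 7 exit procedures.

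**The concern.** Carrying a clear grade forward assumes that the eye would still have been clear at the endpoint visit. For a subject who left because of an adverse event, nobody checked, and that subject will not complete the treatment course under study. The plan already declines to make this assumption for exits due to lack of efficacy, but makes it for exits due to harm. The rescue rule need not catch these subjects: the visible rescue criteria concern anterior chamber cells and severe ocular pain, so an exit for another kind of adverse event can occur without rescue.

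At stake is the content of the primary responder rate, and possibly the result of a close comparison. Under SAP 2.5, inference on pain for a dose is made only if that dose has beaten vehicle on cells, so an error in the cells result also affects whether pain is tested.

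**Working it through.** **Step 1: follow one subject through the rules.** Suppose the last examination is Visit 5 (Day 8) with no cells, no rescue is given, the subject leaves for an adverse event on Day 10, and no later grade is available.

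- Discontinued for lack of efficacy? No; the recorded reason is an adverse event.
- Rescue medication received? No.
- The missing Visit 6 grade is therefore among all other missing data, so the Day 8 grade is carried forward and classified as cells absent.

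The subject is a Day 15 success. All five conditions are needed: exit from the study rather than from the drug alone, an adverse event as the reason, no rescue, no Visit 6 value, and a clear last grade. If the last grade showed cells, carrying it forward already gives a failure. For pain, the exit must come before Visit 4, within the first days of dosing.

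**Step 2: could redacted text add a third failure case?** There is a redaction in SAP 13.1 just after the failure rule. Protocol 11.7 is legible and names only two cases, and SAP section 16 reports no departure from it, so a hidden adverse-event case there is unlikely.

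**Step 3: size.** The plan's power, response rates, alpha, test and allocation are redacted, so there is no planned figure to reproduce. Assumptions: about 150 subjects (Protocol 6.1) in three equal arms, n = 50 per arm; two-sided Pearson test at 0.05 without continuity correction. One subject moves an arm by 1/50 = 2.0 points. With a successes on active and v on vehicle,

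z = [(a − v)/50] / √[p(1 − p) × 2/50], where p = (a + v)/100.

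Example, 25 vs 14: p = 0.39, z = 0.22/√(0.39 × 0.61 × 0.04) = 0.22/0.0975 = 2.26, P = 0.024.

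P-values when k active-arm successes are reclassified as failures and none on vehicle:

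| Active vs vehicle under LOCF | k=0 | k=1 | k=2 | k=3 |
|---|---|---|---|---|
| 25/50 vs 14/50 | 0.024 | 0.039 | 0.062 | – |
| 25/50 vs 12/50 | 0.007 | 0.012 | 0.021 | 0.035 |
| 22/50 vs 10/50 | 0.010 | 0.017 | 0.029 | 0.047 |
| 30/50 vs 15/50 | 0.003 | 0.005 | 0.009 | 0.015 |

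Only the first row crosses 0.05.

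**Step 4: direction.** Start again from 25/50 vs 14/50.

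- One such exit in each arm gives 24/50 vs 13/50: the difference stays at 22 points, z = 0.22/√(0.37 × 0.63 × 0.04) = 2.28, P = 0.023.
- One on vehicle only gives 25/50 vs 13/50: z = 0.24/√(0.38 × 0.62 × 0.04) = 2.47, P = 0.013.

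The present rule can therefore help or hurt OCS-01, depending on where the exits fall.

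**The case against.** **The planned sensitivity analyses cover this.** Protocol 11.7 commits to observed-data, multiple-imputation and tipping-point analyses. This stands in part. The tipping-point analysis can reach the case where these subjects are failures. The observed-data run leaves them out, and no visible text scores them as failures. The detail of SAP 13.1.1 is redacted, so such a run cannot be said to be absent. None of these analyses changes what the primary rate counts.

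**The group is very small.** This stands. Follow-up continues after the drug is stopped, and the exit procedures include a cell and flare assessment. The visible text does not say whether that examination feeds LOCF; if it does, the carried value is more recent but still not from Day 15.

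**Scoring these exits as failures is an estimand preference, and only a partial one.** This stands as a limit. An eye last seen clear may well have stayed clear, and a subject who stops the drug for the same adverse event but remains in the study is scored on observed data and can be a success. The proposal removes unexamined successes; it does not turn intolerance as such into failure.

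**A stronger reading.** A reader might infer that the rule favours OCS-01, because Protocol 3.1 says of the earlier formulation that "the only AE reported has been a modest rise in intraocular pressure (IOP), a known side effect of dexamethasone use". The documents do not support that. The same passage says the rise was modest and subsided when the drug was stopped, and it reports no study exits. Subjects who stop the drug are still examined at Visit 6. Bias toward OCS-01 is possible but not shown.

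**Conclusion.** The gap is real and follows from legible text: an unrescued exit for an adverse event with a clear last grade, or no pain, becomes a primary-endpoint success without an examination at the endpoint visit. The effect is up to 2 points per subject in the arm concerned, on the assumed 50 per arm. It would alter the conclusion only in a result close to the threshold: two subjects in one illustrative scenario, and not three in the other three. Those scenarios rest on assumed arm sizes, test, alpha and rates, and on no such exits under vehicle. The documents give no expected number of these exits and do not establish a direction. The change is worth making because it is cheap and settles in advance how the primary rate treats these subjects, not because the present rule is shown to threaten the trial's result.

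**What to change.** Before unmasking:

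1. Add to SAP 13.1 and 8.2.2 that, in all arms, a missing endpoint value after discontinuation from the study because of an adverse event in the study eye, or one suspected to be related to study drug, is imputed as failure in the primary analysis. Keep LOCF for the remaining reasons.
2. Retain the present LOCF rule as a sensitivity analysis.
3. Record the departure from Protocol 11.7 in SAP section 16, which otherwise becomes untrue. SAP section 1 says that its methods supersede those of the protocol, so the change can be made there.

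The cost is one rule in two places, one entry in section 16 and one extra run. Relatedness, eye and discontinuation reason are already collected. The downside is that an arm's response rate falls by up to 2 points for each such subject, some of whose eyes may in fact have stayed clear. Subjects who stop the drug for an adverse event but stay in follow-up are still scored on observed data.

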- Use of rescue medication on or prior to each visit and overall.

Safety Measures:

- Change from baseline of pin-hole VA (without any other correction) as measured on the ETDRS chart;
- Change from baseline of IOP;
- Adverse event (AE) rates.

Rescue Criteria:

- Grade [REDACTED] anterior chamber cells [REDACTED];
- Severe ocular pain at Visit 4 (Day 4) (or after) with oral acetaminophen.

General Statistical Methods and Types of Analyses:

Full Analysis Set: [REDACTED]

Per Protocol Population: [REDACTED]

Safety Population: [REDACTED]

Hypotheses

Primary Endpoint:

[REDACTED]

Hierarchical Primary Endpoint:

[REDACTED]

Sample Size Determination

[REDACTED]

General Considerations

[REDACTED]

Handling of Missing Data

[REDACTED]

Demographics

[REDACTED]

Primary Efficacy Analysis

[REDACTED]

Secondary Efficacy Analysis:

[REDACTED]

Safety Analysis:

[REDACTED]

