6.4 Exclusion Criteria

Each subject must not:

1. Have a known sensitivity or allergy to dexamethasone, corticosteroids, or any of the study medication's components;
2. Be monocular;
3. Have any intraocular inflammation (e.g. white blood cells or flare) present in either eye [REDACTED]
[REDACTED]
4. Have a score [REDACTED] on the Ocular Pain Assessment at [REDACTED]
[REDACTED]

5. Use anti-inflammatory agents, analgesics/pain relievers (including opioids, narcotics, and other pain medications), or immunomodulating agents, systemically or in either eye, and/or currently using or have any history of use of medications for benign prostatic hyperplasia (BPH) from the washout period through the duration of the study. Washout periods for medications prior to the day of cataract surgery are as follows:

- a. Topical ocular steroids: 14 days;
- b. Periocular injection of any corticosteroid solution: 28 days;
- c. Intraocular treatment with a corticosteroid including dexamethasone drug delivery systems: 56 days after implantation; fluocinolone acetonide drug delivery systems: 48 months after implantation; any other intravitreal injection: 95 days after injection;

Note: While it is expected that subjects requiring an intraocular treatment with a corticosteroid will be excluded due to underlying exclusionary conditions, subjects who otherwise meet all eligibility criteria will be required to follow the above-mentioned washout intervals.

- d. Any systemic treatment with a corticosteroid including oral: 14 days; systemic or parenteral sustained/extended release: 180 days;

Note: Inhaled, intranasal, and topical dermatologic steroids (except on the face and periocular region) are allowed. Topical dermatologic steroids on the face and periocular region require a 7 day washout.

- e. Topical ocular NSAIDs: 7 days;
- f. Systemic analgesics/pain relievers (e.g. gabapentin, pregabalin, and opioids): 14 days;

Note: Use of an opioid during cataract surgery is allowed;

- g. Systemic acetaminophen, NSAIDs, acetylsalicylic acid, or other anti-inflammatory agents: 7 days;

Note: Use of up to 81 mg of acetylsalicylic acid dosed once daily is allowed if dosage has been stable for at least 30 days prior to surgery and will remain stable for the duration of the study.

- h. Medications for BPH (e.g. alpha adrenergic blocking agents including tamsulosin, silodosin, alfuzosin, and finasteride): all current or previous use of BPH medications excludes participation in this study. ;

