9.2.1 Prohibited Medications/Treatments

Prohibited medications and washout periods are summarized in [Table 1](#).

- Ocular surgical intervention scheduled on the contralateral eye within 3 weeks post-cataract surgery; or corneal or retinal surgery (laser or incisional) in the study eye within 6 months of Visit 1 (Day -1 to Day -28 [prior to surgery]); or laser or incisional surgery during the study period in the study eye (other than cataract surgery);
- Use of a contact lens or a collagen shield 72 hours prior to Visit 2 (Day 1 [18 to 30 hours post-surgery]) and for the remainder of the study period in either eye;
- Use anti-inflammatory agents, analgesics/pain relievers (including opioids, narcotics, and other pain medications), or immunomodulating agents, systemically or in either eye, and/or currently using or have any historic use of medications for benign prostatic hyperplasia (BPH) from the washout period through the duration of the study;
- Non-diagnostic topical ophthalmic medications in either eye for the duration of the study with the exception of the following mydriatics, anesthetics, antiseptics, balanced salt solution, viscoelastics, prophylactic antibiotics, non-prostaglandin analog IOP lowering agents, lid scrubs, or artificial tears (allowed topical medication should not be instilled at the same time as the study drug. Study medication should be instilled at least 30 minutes after any prior allowed topical medication. In addition, any other allowed topical medication should not be instilled within 2 hours following instillation of study medication);
- Planned use of anterior capsule staining for capsulorhexis (i.e. trypan blue) during cataract surgery;
- Concurrent enrollment or enrollment within the follow-up period in another study drug or device study is not allowed.

Table 1: Non-allowed Medications and Washout Periods

Medication	Washout Period
Topical ocular steroids	14 days
Periocular injection of any corticosteroid solution	28 days
Intraocular treatment with a corticosteroid	56 days after implantation
Fluocinolone acetonide drug delivery systems	48 months after implantation
Intravitreal injection	95 days after injection
Systemic treatment with a corticosteroid including oral	14 days
Systemic or parenteral sustained/extended release corticosteroid	180 days
Topical ocular NSAIDs	7 days
Systemic analgesics/pain relievers (e.g. gabapentin, pregabalin, and opioids)	14 days

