11.5.2 Primary Efficacy Analysis

Primary Efficacy Measure: The hierarchical primary efficacy measures are the absence of anterior chamber cells [REDACTED]

Primary Efficacy Analysis: The primary efficacy variables, the absence of anterior chamber cells at Visit 6 (Day 15) and the absence of pain at Visit 4 (Day 4), [REDACTED]

[REDACTED]

[REDACTED]

[REDACTED]

[REDACTED]

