13.2.5 RESCUE MEDICATION USAGE

Rescue medications are defined for analysis as those concomitant medications where the eCRF question,

[REDACTED] is answered [REDACTED]
[REDACTED]
[REDACTED]

Rescue medication will be listed by subject and medication.

14. Safety Analyses

All safety analyses will be conducted using the [REDACTED].

Analyses will be presented by treatment group. An additional “OCS-01 Total” group, consisting of all subjects in either OCS-01 treatment group, will also be included.

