14.6 Clinical Laboratory Data

Results from the urine pregnancy test at Visit 1 (Day -28 to -1) and Visit 7 (Day 22) will be listed by subject.

15. Interim Analyses

Interim analyses will not be performed.

16. Changes from Protocol-Stated Analyses

There are no changes from the protocol-stated analyses.

17. References

Allison, P. D. Missing Data. *Sage University Paper Series: Quantitative Applications in the Social Sciences*; no. 07-136: Sage Publications Ltd. 2001.

[figure not shown]
Wilson, E. B., Hilmerty, M. M. The distribution of chi-square. *Proceedings of the National Academy of Sciences of the United States of America*, 17, 684-688. 1931.

18. Revision History

Documentation of revision to the SAP will commence after approval of the final version 1.0.

19. Tables

Tables that will be included in the topline delivery are shown in boldface font.

20. Listings

21. Figures

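### Does the plan leave a Visit 4 pain-free score uncorrected when the subject took an analgesic for eye pain that was not recorded as rescue?

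*SAP*

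**What the plan says.** Protocol 11.5.2 names the two primary efficacy variables: "the absence of anterior chamber cells at Visit 6 (Day 15) and the absence of pain at Visit 4 (Day 4"). SAP 2.5 tests pain for a dose only after that dose has beaten vehicle on cells.

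In SAP 13.1 two events turn a cell result into a failure: a missing value after discontinuation for lack of efficacy, and any value obtained after rescue medication. Pain "will follow the same approach for handling of missing data and handling of pain scores obtained following use of rescue medication". SAP 8.2.2 and Protocol 11.7 use the same two triggers. The observed-data sensitivity analysis in Protocol 11.7 keeps them, "imputing data from subject visits after discontinuation for lack of efficacy or receipt of rescue medication as failures".

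The synopsis gives the pain-rescue criterion as "Severe ocular pain at Visit 4 (Day 4) (or after) with oral acetaminophen". Protocol 3.4.1 mentions rescue for severe ocular pain without naming a visit. In Protocol 6.5 and 9.2.2 the timing is redacted.

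For analysis, SAP 13.2.5 goes by the case report form: "Rescue medications are defined for analysis as those concomitant medications where the eCRF question" is answered in a given way. The question and the answer are both redacted.

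Outside rescue, Protocol 9.2.1 prohibits subjects to "Use anti-inflammatory agents, analgesics/pain relievers (including opioids, narcotics, and other pain medications), or immunomodulating agents, systemically or in either eye" through the end of the study. Protocol 6.4 lists among the washouts "Systemic acetaminophen, NSAIDs, acetylsalicylic acid, or other anti-inflammatory agents: 7 days".

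**The concern.** Rescue given under the synopsis criterion cannot change the Visit 4 pain result. A subject with severe pain at Visit 4 has already failed, and one rescued later has already been assessed. The rule that protects this endpoint thus seems to have nothing to act on. Acetaminophen is both the named rescue drug and, outside rescue, a prohibited one, so the same tablet taken for eye pain on Day 2 could make the subject a failure or leave an observed success, depending on how the form was completed.

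The sensitivity analyses named in Protocol 11.7 do not obviously help. Observed-data and per-protocol analyses keep the same triggers, while tipping-point and multiple-imputation analyses deal with missing values, and a score observed after an analgesic is not missing. SAP section 16 adds "There are no changes from the protocol-stated analyses", which could be read to mean that nothing further is planned. At stake would be the interpretation of the second primary endpoint, since part of a pain-free rate could reflect analgesic use and not study drug.

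**Working it through.** **Step 1. What triggers a failure.** The trigger is the rescue entry on the form (SAP 13.2.5), with no visit attached. A pre-Visit 4 analgesic recorded as rescue already makes the Visit 4 score a failure. Cell rescue, whose timing is redacted, could also come first. Only an analgesic not recorded as rescue is left open, and whether the form question would catch it depends on redacted words.

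**Step 2. What visibly applies to such an analgesic.**

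| Place | What it provides |
|---|---|
| Protocol 9.2 and 9.3 | All concurrent medication is recorded with its reason; a medication update is scheduled at Visit 4 |
| Protocol 9.2.1 | Non-rescue analgesics are prohibited, so use is a deviation |
| SAP 6.1 and 8.4 | Deviations are graded major or minor before unmasking |
| SAP 13.1.1 | Primary analyses are repeated under other handling of missing data and of major deviations; detail redacted |
| SAP 11.2 | Non-ocular drugs that could affect cell count or ocular pain are found by manual review of drug class and indication, and treated as ocular |
| SAP 13.1.2 | A masked review of all medications classifies subjects for subgroup analyses of the primary analysis; categories redacted |

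The plan therefore collects the information, looks for pain-relevant drugs by indication, classifies subjects while masked, and reruns the primary analyses with deviations handled differently.

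**Step 3. Does SAP section 16 close the list?** No. SAP section 1 says its methods supersede those in the protocol, and the SAP contains analyses that Protocol 11.7 does not name, such as the subgroup analyses in 13.1.2. A statement of no changes does not show that the redacted part of 13.1.1 is limited to Protocol 11.7.

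**Step 4. Size, for illustration only.** The plan's rates, alpha, power and allocation are redacted, so none of its figures can be reproduced. Assumptions: about 150 subjects split equally, giving 50 per arm; two-sided 5%; true pain-free rates of 30% on vehicle and 60% on active; a share u of subjects in pain takes an analgesic, and half of them then score zero.

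Observed rate = p + (1 − p) × u × 0.5. At u = 10%, vehicle is 0.30 + 0.70 × 0.10 × 0.5 = 0.335 and active is 0.60 + 0.40 × 0.10 × 0.5 = 0.62. Power is from the two-proportion normal approximation with pooled null variance.

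| Use, vehicle / active | Observed rates | Difference (points) | Power |
|---|---|---|---|
| 0% / 0% | 30% / 60% | 30 | 87% |
| 5% / 5% | 31.75% / 61% | 29.25 | 85% |
| 10% / 10% | 33.5% / 62% | 28.5 | 82% |
| 20% / 20% | 37% / 64% | 27 | 78% |
| 20% / 10% | 37% / 62% | 25 | 71% |
| 5% / 10% | 31.75% / 62% | 30.25 | 87% |
| 0% / 20% | 30% / 64% | 34 | 94% |

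The difference is unchanged when 0.70 × u(vehicle) = 0.40 × u(active), that is, when use among subjects in pain on active is 0.70 / 0.40 = 1.75 times that on vehicle. Below that ratio the effect is diluted. Above it the effect is inflated, and not always slightly: the last row adds 4 points.

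**Step 5. Cost of scoring all takers as failures.** Such scoring also fails subjects who would have been pain-free anyway. If a share u of them is caught, each rate becomes p × (1 − u):

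| Pain-free subjects also failed | Rates | Power |
|---|---|---|
| 5% | 28.5% / 57% | 83% |
| 10% | 27% / 54% | 79% |
| 20% | 24% / 48% | 71% |

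At equal percentages this loses at least as much power as the dilution it is meant to remove.

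**The case for a change.** The best opposing case is that the visible text never says how a zero score after an unrecorded-as-rescue analgesic is handled. SAP 11.2 reclassifies such drugs as ocular but does not link that to endpoint scoring. SAP 13.1.1 covers deviations, but nothing visible says this use would be graded major, and setting a subject aside is not the same as scoring a failure. With about 50 per arm, single subjects can matter: 20/50 against 30/50 gives p = 0.046 by uncorrected chi-square; re-scoring one active subject as a failure gives 0.072, and re-scoring one vehicle subject gives 0.028. Settling the rule before unmasking would cost little.

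Much of this stands as fact. The synopsis timing does leave pain rescue with almost no role in the Visit 4 score, and borderline results are sensitive to one or two subjects in either direction. It does not establish a defect. The words that would decide the matter are redacted: the form question, the detail of 13.1.1, the categories in 13.1.2 and the per-protocol definition in SAP 7.3. Text withheld from the public copy cannot be counted as absent from the plan. Preferring failure scoring to another handling of deviations is a choice between defensible options. Leaving a non-rescue analgesic as observed in the full analysis set is one of them in a Phase 2 trial.

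**Conclusion.** The concern does not hold. The mismatch in timing between pain rescue and the pain endpoint is real, but it does not show a scoring gap: rescue is identified by the form entry and not by visit, and use outside rescue is a prohibited-medication deviation in a plan that includes a masked medication review and a rerun of the primary analyses for major deviations. What is left is detail that the public copy withholds, together with an optional extra analysis that would leave the primary analysis unchanged.

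Under the stated assumptions, equal analgesic use by 5% to 20% of subjects in pain would lower power from 87% to 85% to 78%, working against OCS-01. Inflation requires use on active above 1.75 times that on vehicle, and nothing in the documents suggests such an imbalance. These figures rest on assumed rates, allocation, alpha and analgesic use; they indicate scale and say nothing about the trial's actual power.
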